## 1. STATEMENT OF COMPLIANCE

This PN-RCT will be conducted in compliance with the International Council on Harmonisation Good Clinical Practice (ICH GCP) applicable United States (US) Code of Federal Regulations (CFR), and the U.S. Department of Health and Human Services' Terms and Conditions of Award. The Principal Investigator will assure that no deviation from, or changes to the protocol will take place without prior agreement from the funding agency and documented approval from the Institutional Review Board (IRB), and the Investigational new behavioral health treatment (BE WITH), if applicable, except where necessary to eliminate any immediate hazard(s) to the trial participants.

All personnel involved in the conducting of this study will have completed CITI training.

The protocol, informed consent form(s), recruitment materials, and all participant materials will be submitted to the IRB for review and approval. Approval of both the protocol and the consent form(s) will be obtained before any participant is consented. Any amendment to the protocol will require review and approval by the IRB before the changes are implemented to the study. All changes to the consent form(s) will be IRB approved; a determination will be made regarding whether a new consent needs to be obtained from participants who provided consent, using a previously approved consent form.

## 1 PROTOCOL SUMMARY

### 1.1 SYNOPSIS

Title:	ADDRESSING SOCIAL ISOLATION, LONELINESS, AND ELEVATED SUICIDE RISK AMONG VULNERABLE OLDER ADULTS THROUGH AN 8 WEEK CARING CONTACTS TREATMENT: A PARTIALLY NESTED RANDOMIZED CONTROLLED TRIAL
Grant Number:	90INNU0021-03-00
Study Description:	
This PN-RCT evaluates an 8-week caring contacts treatment that is delivered to older adults (urban racially diverse, suburban, and/or rural) in 20-30 minute warm calling "dosages", over 3 conditions. Conditions include 2 treatment (i.e. treatment provided by helpers trained in a standardized and manualized Belongingness and Empathy training grounded in narrative reminiscence and the befriending literature (BE), and treatment provided by helpers trained in BE plus a standardized, manualized, and evidence-based suicide intervention training, the Aging Variant of LivingWorks ASIST (BE WITH), and 1 control (no treatment). Hypotheses include: (a) participants in the BE and BE WITH treatment conditions will experience significantly more improvement across measures than those in the control condition over the course of the 8-week treatment and (b) outcome improvements for those in treatment conditions will be more pronounced for those who begin the period at greater risk.

Objectives * :	
Primary Objective: To develop BE WITH Innovation and equip the Aging Services Network (ASN) with proven skills to reduce social isolation, loneliness, and elevated suicidality and promote social support/well-being with older adults receiving nutrition services.
 
Secondary Objectives: To validate and replicate BE WITH

Endpoints * :	
Primary Endpoint: Reduction in social isolation, loneliness, and elevated suicidality and improved social support/well-being for older adult participants receiving nutrition services.
 
Secondary Endpoints: Improved frequency of empathic and suicide intervention best practice behaviors by trained volunteers

Study Population:	Target $n = 540$ to adequately power the PN-RCT; men and women, aged 65 or older, receiving nutrition services, without instance of dementia or cognitive impairment, and in the state in the Southeastern US.
Description of Sites/Facilities Enrolling Participants:	There will be three Area Agencies on Aging, and 25 senior centers that will be involved in this clinical trial.

**Description of Study  
Intervention/Experimental  
I Manipulation:**

[figure not shown]
The 8-week warm calling treatment is delivered to older adults in 20-30 minutes, once a week by phone call, over three conditions: BE, BE WITH, and control. The BE condition involves receiving services from providers trained to foster belongingness and empathy. The BE WITH condition includes the BE training as well as the aging variant of LivingWorks ASIST (Applied Suicide Intervention Skills Training).

**Study Duration\*:** 24 months

[figure not shown]
**Participant Duration:** 2 months

## 1.2 SCHEMA

*Example #1 Flow Diagram (e.g., randomized controlled trial)*

Based on the NIH Protocol Template for Behavioral and Social Sciences Research

### 1.3 SCHEDULE OF ACTIVITIES

	Week 0	Week 1	Week 2	Week 3	Week 4	Week 5	Week 6	Week 7	Week 8	Week 9
MOUs with AAAs and senior centers	X									
Secure Lists of Potential Participants From Senior Centers	X									
Recruitment Phone Calls		X								
Baseline Survey		X								
Scoring of Baseline Survey		X								
Random Assignment to 3 Conditions		X								
Phone Calls Back to Participants with Corresponding Consent (BE, BE WITH, Control)		X								
Measurement Occasions				X		X		X		X
Call Dosages			X	X	X	X	X	X	X	X

## 3. 2 INTRODUCTION

### 1. 2.1 STUDY RATIONALE

Social isolation and loneliness are prevalent among older adults, detrimental to their health and well-being, and can lead to suicide. While 24% of community-dwelling older adults in the United States are socially isolated, almost half of older adults report feeling lonely. Loneliness and social isolation have deleterious effects on older adults' physical and mental health, including elevated risk of dementia, hopelessness, anxiety, and increased morbidity. When older adults feel like they do not belong (thwarted belongingness), and that they are a burden to others (perceived burdensomeness), desire for suicide increases. An older adult dies by suicide every 65 minutes. Yet these data only reflect officially reported suicides; many more are categorized incorrectly and/or go unreported (e.g., overdose, voluntary stopping of eating and drinking, withholding medical treatment). Social isolation, loneliness, and elevated suicidality (SILES) were exacerbated by the COVID-19 pandemic. In addition to elevated physical health risks, older adults face deleterious psychological *and* social impacts from the disease. Social support is one of the strongest predictors of positive psychological outcomes during disaster.

### 2. 2.2 BACKGROUND

**Applied Suicide Intervention Skills Training (ASIST)**, a standardized, manualized,

Based on the NIH Protocol Template for Behavioral and Social Sciences Research

internationally recognized training developed by LivingWorks, has been adopted by the U.S. Armed Forces, and the Centers for Disease Control. Grounded in a public health framework, ASIST prepares *natural helpers* to facilitate life-assisting interventions at the moment needed. ASIST is the only evidence-based *intervention* training that has been found to reduce suicidality in real time. Emphasis is placed on the “*quality of the interaction between the natural helper and the person-at-risk*,” with a focus on how that connection can reduce risk while connecting the person with resources. ASIST-trained helpers learn to address a variety of emotional disturbances, and its intervention model (i.e., pathway for assisting life) can be generalized to work with additional challenges such as social isolation and loneliness. In some instances, ASIST has been found sufficient to keep the person-at-risk safe, with no further need for dedicated mental health services. ASIST-saturated hospitals, school systems and military contexts have reported **reduced suicides, more brief interventions, and fewer referrals** to other services. ASIST is appealing to the ASN, as it is **not** likely to increase the need for coordinating official mental health treatment as older adults are getting needs met in real time.

ASIST equips volunteers with intervention skills that keep them from feeling “immobilized” and unsure of how to help when they feel something is wrong with their older adult clients, which may prevent burnout. ASIST trained nutritional service (NS) volunteers are ready, willing, and able to ask directly about suicide, understand the stressors in client’s life, work effectively with ambivalence about dying, identify reasons for living, and create a mutually agreed upon safe plan (see Appendix C). In spite of its merits, ASIST was not developed with older adults in mind, and outcomes have not yet been rigorously evaluated in the ASN context. Similar to the augmented version of ASIST for the military, LivingWorks has agreed to work with us to adopt a new **aging specific variant of ASIST** (see letter of support). Modifications include video scenes of warning signs in older adults (i.e., voluntary stopping of eating and drinking), understanding thwarted belongingness and perceived burdensomeness in later life, and role plays relevant to working in the nutrition context. Trained NS volunteers will be able to identify and respond to the unique situations they may face during HDM, and now in other socially distanced communications with older adults.

**Phone-based Belonging through Empathy (BE) Training** will be a brief, online module to guide NS volunteers in how to foster a sense of belonging for older adults through empathic, engaged listening (see Appendix B). Concrete tips are provided for ensuring calls are conducted in a manner that fosters *relationships* -- putting natural helpers into the lives of older adults. People who are connected and feel understood are at less risk for suicide than those who are isolated. Belonging is a powerful reason for living among older adults, and its absence is a proven risk factor for suicide. Empathy consists of genuinely engaging, recalling details from previous conversations, and maintaining composure and care when painful material is identified. Developments in biology and neuroscience routinely show that empathy is a core building block of human connection, making it an essential skill for volunteers to develop and employ when speaking with older adults. By equipping NS volunteers to promote a sense of belonging through empathic techniques such as active listening, building trust, and communicating a sense of mattering, we aim to reduce social isolation, loneliness, and elevated suicidality for HDM recipients and former CM clients.

### 3. 2.3 RISK/BENEFIT ASSESSMENT

#### 1. 2.3.1 KNOWN POTENTIAL RISKS

In the short term, there is the possibility that participation in this project may cause older adult participants to feel some worry or concern - for example, they may be asked about how they have been coping, and this may bring up feelings of anxiety. However, research has shown that talking about stressful life events provides opportunities to receive support and actually reduce stress. If participants experience any concerns,

the informed content specifies that study personnel are available to answer any questions they may have and to provide support. Another known risk is the possibility of the participants feeling a sense of loss once the study is over as they will have built relationships with their calling providers.

In the long term, there are no risks affiliated with participation in this study.

## 2.

### 2.3.2 KNOWN POTENTIAL BENEFITS

**Immediate potential benefits:** Social support has been proven across hundreds of behavioral health studies to be one of the strongest predictors of positive psychological outcomes following disaster. Research has also shown that connecting with others during crisis, disaster (i.e. pandemic) is helpful in the immediate. Across disasters talking about, expressing, and feeling one's feelings has been found to set persons apart from those that do not in terms of faring better as a result of experiencing crisis/disaster.

**Long term potential benefits:** Overall, we hope to gain information about the BE WITH innovation, and ideally submit BEWITH to be accepted on the National Council on Aging's (NCOA) evidence-based registry to enable warm calling programs to occur across the US. Currently, there is no program to make warm calls, or visits remotely on the NCOA registry, so the older adult participants in this study will be made aware (in the informed consent) of this larger purpose and that they are helping contribute to bringing these types of warm calling programs to older adults across the country.

## 3.

### 2.3.3 ASSESSMENT OF POTENTIAL RISKS AND BENEFITS

Older adults are the highest risk age cohort for suicide however the least likely to receive intervention. Creating an opportunity to receive an 8-week caring contacts intervention may be a standardized and measurable means of catching those at risk and responding to them in real time. While any risk to participants for participation is deemed extremely low, assessment questions might create some feelings of discomfort. Providing the assessment questions is a necessity for tracking mental health variables (including suicidality) as well as being able to measure the impact of the treatment across conditions.

The value of the information gained outweighs any risk of participation. Older adults at risk will receive 8 weeks of standardized and manualized warm calls, potentially with intervention if at risk of suicide, and the knowledge learned will enable us to get this treatment on NCOA's evidence-based registry. This will enable AAA's (Area Agencies on Aging) and senior centers throughout the country to use Title 3D dollars to put this program into their contexts to respond to older adults experiencing mental health distress and better respond to the problem of suicide in this population.

## 4. 3 OBJECTIVES AND ENDPOINTS

Objective	Metric/Variable	Hypothesis/role/endpoint	Analysis
-----------	-----------------	--------------------------	----------

Validate the BE WITH innovation	Reduce loneliness, and elevated suicidality, and increase the degree to which social needs are met	Over the 8-week treatment loneliness and suicide desire (as measured by the UCLA loneliness scale, Interpersonal Needs Questionnaire) will be significantly decreased, and the variable of social needs being met (as measured by the social provisions scale) will be increased for both treatment groups	Longitudinal growth modeling
Validate the BE WITH innovation	Three treatment conditions	Those older adult participants randomly assigned to the BE or BE WITH treatment condition will demonstrate significant improvements in mental health outcomes when compared with the control group	Longitudinal growth modeling
Validate the BE WITH innovation	Risk tier	Those older adults that start the 8-week treatment at medium or high risk will have statistically significant improvements when compared with those of low risk	Longitudinal growth modeling
Validate the BE WITH innovation	Provider effects	Determine if there is variance in outcomes as a result of the provider assigned. 60 providers were trained in either BE or BE WITH and carried caseloads of older adult clients enabling the nesting of effects to determine if there are individual or group level provider effects	Multilevel modeling
Validate the BE WITH innovation	Improved quality, frequency of empathic and suicide intervention best practice behaviors by trained NS providers	An augmented version of Gould's (2013) coding protocol was developed to quantitatively behaviorally code treatment call dosages.	independent quantitative behavioral coding, double coding, 2 protocols, inter-rater agreement, coefficient kappas

The main overarching objective of the clinical trial is to validate the 8-week BE WITH warm calling program, equipping the Aging Services Network (ASN) with proven skills to reduce social isolation, loneliness, and elevated suicidality, while also promoting social support/well-being. The goal of the validation objective is to garner the evidence needed to get the first such program on the National Council on Aging's Evidence Based Registry.

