				Relative validity estimates for 12-item MCS ranged from 0.60 to 1.07 (median = 0.97) in relation to 36-item short-form scale		
Interpersonal Needs Questionnaire	INQ-15	Suicide Desire-thwarted belongingness scale only	All time points	
Reliability: Thwarted Belongingness - Cronbach's alpha: ~ 0.85
 
Good construct validity (thwarted belongingness correlated significantly with loneliness and low social support) and criterion-related validity (thwarted belongingness uniquely predicts current suicidal ideation: odds ratio = 1.59, <math>p < .01</math>)
	15 items (8 TB)	Category 3: Health and Well-being

*\*\*Please review the table below for a summary of the main mental health measures utilized in this PN-RCT.*

Participant screening includes administration of the UCLA, INQ, and SPS, scoring them, and assigning a risk tier. Participants that are middle or high risk will be enrolled in the trial, whereas those that are low risk do not meet eligibility and will be called back to clarify/answer any questions they may have. Measures will be scored the same day, risk tiers and randomization assigned the same day, whereas the call backs to participants may take up to 72 hours.

Trained graduate student data collectors will be administering all assessments via the phone verbally to older adults. Each received training and administered the measure set, was provided with feedback, and made adjustments to ensure that the measures were administered with fidelity across the trial. Further,

there were notations in Qualtrics to indicate reverse coded items, etc., in which wording may be particularly confusing to older adults to remind data collectors to slow down, repeat, and/or rephrase to ensure that the older adult understood each and every item.

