## 11. 9 STATISTICAL CONSIDERATIONS

### 1. 9.1 STATISTICAL HYPOTHESES

**Primary Endpoint(s):**

We hypothesize that older adults in both calling conditions will have reduced: social isolation, loneliness, depression, anxiety, mental health distress, and suicide desire; and they will have increased: social connection, social support, and well-being over time and in comparison to those in the control condition.

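### Section 3 lists a change within the treated arms and a comparison between risk tiers as validation hypotheses, neither tied to the control arm, so regression to the mean could satisfy either one without a treatment effect

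*Combined protocol and SAP*

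**What the plan says.** The Section 3 table has five rows, all under the objective of validating BE WITH.

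- **Row 1** predicts that loneliness (UCLA) and suicide desire (INQ) "will be significantly decreased, and the variable of social needs being met" (SPS) "will be increased for both treatment groups". No control is mentioned.
- **Row 2** is the randomized comparison: people assigned to BE or BE WITH "will demonstrate significant improvements in mental health outcomes when compared with the control group".
- **Row 3** reads: "Those older adults that start the 8-week treatment at medium or high risk will have statistically significant improvements when compared with those of low risk". Neither arm nor control is mentioned. The Synopsis has a version restricted to treated people: "outcome improvements for those in treatment conditions will be more pronounced for those who begin the period at greater risk".

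Section 8.1 says that screening consists of giving and scoring the UCLA, INQ and SPS and assigning a tier. It continues: "Participants that are middle or high risk will be enrolled in the trial", and says low-risk people are not eligible. Section 6.3 also assigns the tier from the scored baseline data, but with three levels (low, medium, high). The Section 4.1 table stratifies on three tiers, and Section 9.4.7 repeats the primary analysis in each of three tiers.

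The control arm is used elsewhere. Sections 4.1 and 9.1 state the hypothesis as change "over time and in comparison to those in the control condition". Section 9.4.2 tests condition while adjusting for baseline. Section 9.4.7 includes interactions between treatment condition and subgroup variables, baseline severity among them. No section mentions regression to the mean.

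**The concern.** People selected or grouped on an imperfectly reliable score tend to move back towards the average when measured again. Here the selecting score is the baseline value of the outcome itself. Untreated people chosen for high loneliness would be expected to score lower at week 8. Untreated people in a high tier would be expected to fall further than those in a low tier.

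Row 1 cannot be read as shorthand for the control comparison, because that comparison has its own row. Row 3, as worded, could be met equally well inside the control arm. The stated aim is evidence for a national registry of evidence-based programmes. A significant within-arm fall, or a steeper fall in higher tiers, could be presented as part of that evidence even if the controls changed just as much.

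**Working it through.** The plan gives no figure for regression to the mean, so there is none to reproduce. Its own planning inputs are used where they exist.

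**Inputs from the plan**
- R² for the baseline covariate .50, so r = √.50 = .707 (Section 9.2)
- 180 per arm, ICC .20, 6 older adults per caller (Section 9.2)
- Significance level .01 (Section 9.4.1); Section 9.2 uses .05, which would give higher rates

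**Assumptions**
- Two-sided test, normal scores, no treatment effect and no time trend
- r applies in the screened population
- The ICC applies to change scores
- Tier cut-offs are not given, so the top two-thirds and the top half are taken as the enrolled range

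**Design effect.** 1 + (6 − 1) × .20 = 2.

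**Row 1, selection on the tested scale.** Expected fall = (1 − r) × λ, where λ is the mean standardized baseline of those enrolled. Change variance = (1 − r²) + (1 − r)² × V, where V is the baseline variance among those enrolled.

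| | Top two-thirds | Top half |
|---|---|---|
| λ | .545 | .798 |
| V | .468 | .363 |
| Expected fall | .293 × .545 = .16 SD | .293 × .798 = .23 SD |
| SD of change | √(.50 + .0858 × .468) = .735 | √(.50 + .0858 × .363) = .729 |
| Fall ÷ [SD × √(2/180)] | 2.06 | 3.04 |
| False decrease at .01, design effect 2 | 30% | 67% |
| Same, no clustering | 62% | 95% |

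At r = .80 the two design-effect-2 rates are 18% and 45%.

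**Row 1, selection on a composite.** Section 8.1 tiers on three scales but gives no scoring rule. Assume an equal-weight sum, inter-scale correlation .50 and cross-time, cross-scale correlation c of .35 to .50. The sum has variance 3 + 6 × .50 = 6.
- Baseline scale with composite: (1 + .50 + .50)/√6 = .816.
- Week-8 scale with composite: (.707 + 2c)/√6 = .574 (c = .35) or .697 (c = .50).
- Expected fall = (difference of these two) × λ. This is .242 × .545 = .13 SD or .120 × .545 = .065 SD for the top two-thirds, and .19 or .095 SD for the top half.
- False decrease with design effect 2: 4-18% (top two-thirds) or 8-45% (top half).

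**Row 3, all three tiers enrolled as equal thirds.** The high and low thirds have mean standardized baselines of ±1.091, a gap of 2.18. The medium/high group and the low third differ by 1.64.
- Tested scale: high versus low .293 × 2.18 = .64 SD; medium/high versus low .293 × 1.64 = .48 SD.
- Composite: high versus low .120 × 2.18 = .26 SD to .242 × 2.18 = .53 SD; medium/high versus low .20 to .40 SD.
- Simulation on a single scale (180 in one arm, no clustering, .01 level): medium/high falsely improve more than low in 93% of trials at r = .72 and 62% at r = .85.

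**Same mechanism, controlled contrasts.** In those simulations the difference in change between randomized arms and the tier-by-arm interaction rejected in 0.6-1.3% of trials at the .01 level, about the nominal rate.

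**Dependence on who is enrolled**

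| | Row 1 | Row 3 |
|---|---|---|
| Low risk excluded (Section 8.1) | exposed | no low-tier comparator |
| All tiers in population proportion | mean change about 0, not exposed | exposed |
| Enriched for high scores, some low risk kept | exposed | exposed |

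**The case against.** The strongest reply is that the statistical section already uses the control arm. Sections 4.1 and 9.1 require change over time and against control, and Section 9.4.2 tests condition adjusted for baseline. Section 9.4.7 plans the baseline-severity interaction, and its tier-by-tier runs repeat the primary analysis with control included. If the controls improved equally, row 2 would not be met. All of this stands: the trial has valid randomized tests. It does not change what rows 1 and 3 say.

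A reader might infer that the trial could be declared validated on rows 1 and 3 alone. The documents do not support that, because no section makes either row sufficient for success.

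A reader might also infer that regression would normally satisfy both rows together. The two exposures need different enrolment. Both arise only in a sample enriched for high scores that still contains low-risk people. Two such samples were simulated at .01 without clustering: equal thirds drawn from a 60/25/15 population, and 10% low-risk drawn from a population of equal thirds. Both rows were falsely met in 3-45% of trials.

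Two further points are fair. Tiering on three scales weakens regression on each one, which is why the composite range is given. The planned analysis is a growth model over five occasions, whereas the calculation is a baseline-to-week-8 comparison, so the rates are indicative.

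**Conclusion.** The concern holds for rows 1 and 3 of Section 3 and no further. Each is a free-standing validation hypothesis without a control contrast, and each can be met by regression to the mean under one of the enrolment rules the document contains.

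With no treatment effect and the assumptions listed, a false within-arm decrease occurs in about 30-67% of trials if selection is on the tested scale, or about 4-45% if it is on the assumed composite. With tertile tiers, high versus low differs by about .26-.64 SD. The cut-offs, the scoring rule and the eight-week correlation are not in the documents, so these are ranges and not predictions. That either row can be met without an effect needs only a baseline-to-week-8 correlation below 1 and the enrolment pattern shown for that row.

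The randomized comparisons are unaffected. Separately, if Section 8.1 is applied strictly, row 3 has no comparator, which conflicts with Sections 3, 4.1, 6.3 and 9.4.7.

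**What to change.** Align Section 3, and hypothesis (b) of the Synopsis, with Sections 9.1, 9.4.2 and 9.4.7.

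1. **Row 1:** state it as the BE-versus-control and BE WITH-versus-control differences in the planned model, either condition × time or the baseline-adjusted post-intervention difference.
2. **Row 3:** state it as the treatment-by-tier interaction (condition × time × tier) among the tiers actually enrolled.
3. **Descriptive only:** report within-arm and within-tier change without counting it as validation evidence.
4. **Enrolment:** reconcile Section 8.1 with Sections 3, 4.1, 6.3 and 9.4.7 on whether a low tier is enrolled, and state the tier scoring rule and cut-offs.

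The cost is wording. The control data and interaction terms are already planned, and no additional data are needed. One limit should be stated: Section 9.2 did not size the trial for a tier interaction, so row 3 in this form may be imprecise.
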